3.0 Objectives

The proposed 4-year, multisite, randomized effectiveness-implementation trial will focus on the real-world application of bCBT for Veterans with depression, as applied by frontline CBOC practitioners. Effectiveness-implementation designs seek to simultaneously test: 1) strategies to improve care practices (e.g. clinician support programs) and 2) examine patient outcomes associated with the clinician program being implemented. The current project will invite mental health clinicians at the Houston and Oklahoma City CBOCs (16 sites) to participate. As part of study participation, providers will receive bCBT training and support from the study. Once trained, these CBOC clinicians will be asked to provide care to a Veteran patient population identified by the study team. Veteran participants from each respective CBOC, identified by study-based screening, will be randomized to a bCBT direct referral arm or to an Enhanced Usual Care (EUC) condition. Direct referral participants will be assigned to a CBOC provider trained by the study team in the use of bCBT. The study will pair providers and patients at each CBOC facility. EUC participants will not receive a direct referral. Rather, these participants will receive depression education materials, a note placed in their medical record indicating the presence of depression, and encouragement to seek services from their existing providers.

Aim 1 – Implementation (training and assisted use of bCBT by frontline CBOC clinicians): The study will use a formal evaluation procedure to capture information on the clinical and implementation efforts as delivered by CBOC providers. Data will be used to modify the clinical training and support program. Known as a formative evaluation, the study will include a developmental assessment to collect data on clinician adoption, intervention fidelity, and individual interviews with stakeholders to obtain a deeper understanding of implementation challenges associated with using bCBT in the CBOC setting.

Aim 2 – Clinical Effectiveness (patient outcomes): To determine whether depression (PHQ-9 and Beck Depression Inventory) and quality-of-life (SF-12) differ as a function of bCBT referral (vs. EUC) at 4-, 8- and 12-month follow-ups.

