5.6 Data Analysis

Sample Size and Power Calculations:

Provider Sample (Implementation Data; Aim 1)

No formal sample size calculations were used for the implementation-focused elements of this project. Rather, the team will invite all CBOC providers at all sites within the HOU and OKC VAMCs to participate and subsequently evaluate how many providers opted to engage in the bCBT project. These procedures are common for implementation-focused trials that often have a smaller pool of “subjects”. Designs of this nature often look less at statistical significance and

instead focus more on descriptive quantitative data and depth interviewing and qualitative analyses to determine impact and “lessons learned”.

Veteran Sample (Effectiveness Data; Aim 2)

Sample-size calculations indicate that 232 patients will need to be randomized to address the primary hypothesis for aim 2. Based upon our current project, we will need to recruit 300 Veterans. Approximately 30% of recruited participants were screened ineligible due to subthreshold anxiety and/or depression scores.

We will use unequal randomization to reduce unnecessary recruitment, resulting in 138 patients for bCBT and 94 for EUC. In determining the sample size, we first determined the number of participants needed to have 80% power to detect significant differences in the primary outcomes between our groups. We then inflated this to account for intraclass correlations among patients and for attrition and loss to follow-up. A sample size of 70 patients in both the bCBT and EUC groups (140 total) is needed to detect a difference in the means of the primary outcome that reflects a small effect size of .30, using a 2-sided *t*-test with 80% power at the .05 significance level, adjusted for repeated measures.⁵⁶ The small effect size was chosen to ensure an adequate sample size to address multiple study aims and outcomes. The bCBT sample size was then inflated by $[1 + (m - 1) c]$ to account for the intraclass correlation due to clustering of patients within bCBT clinicians.⁵⁷ Based on the sample size of 70 bCBT patients, an average of 5.8 patients per therapist, and an assumed correlation, *c*, among patients of .10,⁵⁷ our inflation factor is 1.48 ($70 \times 1.48 = 104$). A clustering inflation factor was not used for the EUC group. Both the bCBT and EUC groups are inflated to account for attrition rate at 12 months of 25%.

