Unequal numbers of patients per group offers the advantage of reduction in unnecessary recruitment. We will have 80% power to detect a clinically important difference in means on the PHQ-9 between the intervention and usual care groups that is as small as 1.83, based on a small effect size of .30 and estimates of the pooled standard deviation of 6.1.⁵⁸ Lowe concluded that differences in PHQ-9 scores of 5 or greater reflect a clinically relevant difference. Similarly, we can detect differences in the means of the BDI between the treatment and EUC arms as small as 3.6 units, assuming a standard deviation of approximately 12 as seen in [name] et al. 2008.³¹ Assuming mean baseline BDI values of 20 or higher,³¹ we will have more than 80% power to detect a 50% reduction in BDI. For quality of life as measured by SF-12, a difference of one-half standard deviation (i.e., 5 points) is considered clinically significant.⁴⁸ On the basis of the standard deviation of the Mental Component Summary score (MCS) from [name] et al.³¹ of 14.7 and from Hendrick et al of 11.5, we will have 80% power to detect a difference in MCS scores as small as 3.45. For the SF-12 Physical Component Summary score, assuming standard deviations of 11 and 12 we can detect a difference in means as small as 3.3 points. Therefore, we will have more than 80% power to find clinically significant differences in quality of life.

Patient Availability: CBOCs in Houston and Oklahoma City care for a large (n = 50,000+) and diverse Veteran population. We estimate a sample of 7,500 assuming a 15% rate of elevated depressive symptoms.

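### The 70 per arm for an effect of 0.30 rests on an unstated repeated-measures assumption and does not support 80% power for Aim 2's visit-specific and time-by-treatment comparisons

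*Combined protocol and SAP*

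**What the plan says.** Section 5.6 (Sample Size and Power Calculations) starts from this statement: "A sample size of 70 patients in both the bCBT and EUC groups (140 total) is needed to detect a difference in the means". The assumed effect is 0.30 SD, which the plan calls small. The test is a two-sided t-test "with 80% power at the .05 significance level, adjusted for repeated measures". The bCBT arm is then multiplied by 1.48 for clustering within clinicians and both arms are inflated for 25% attrition at 12 months, "resulting in 138 patients for bCBT and 94 for EUC".

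The same section converts 0.30 into points for each outcome: 1.83 on the PHQ-9 (SD 6.1), 3.6 on the BDI (SD about 12), 3.45 on the SF-12 MCS (cited SDs 14.7 and 11.5) and 3.3 on the PCS (SDs 11 and 12). It takes 5 points as clinically significant on the SF-12 and concludes: "Therefore, we will have more than 80% power to find clinically significant differences in quality of life".

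Section 3.0 sets Aim 2 as whether outcomes "differ as a function of bCBT referral (vs. EUC) at 4-, 8- and 12-month follow-ups". The Aim 2 analysis in section 5.6 is a longitudinal mixed model in which the time-by-treatment interaction carries the group comparison. Baseline score is not named as a covariate.

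**The concern.** The inputs printed in section 5.6 do not lead to 70. The step down from about 175 is put down to repeated measures, but the number of measures, the within-patient correlation and the contrast are all missing. How much repeated measures save depends on what is being estimated. An average over several visits can gain a great deal, while a comparison at one visit gains only through its correlation with baseline. Aim 2 names visits, and the model tests an interaction. Neither is an average over visits.

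The 0.30 is then multiplied by each SD as though it applied to any difference in means. A reader who takes 80% power for 1.83 PHQ-9 points at 4, 8 or 12 months from this section could give a null result at that visit more weight than the design supports. The quality-of-life claim is the most exposed, because its 5-point threshold lies close to what one visit can detect.

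**Working it through.** **Inputs from section 5.6:** d = 0.30, two-sided alpha 0.05, power 80%, 70 per arm, inflation 1.48, attrition 25%, and the SDs above. The documents give no correlation, so every ρ below is an assumption. Compound symmetry is assumed throughout.

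**1. Reproducing the plan's chain.**
- Clustering: 1 + (5.8 − 1) × 0.10 = 1.48, and 70 × 1.48 = 103.6, or 104.
- Attrition: 104/0.75 = 138.7 (stated 138) and 70/0.75 = 93.3, or 94. Total 232.
- These steps agree apart from rounding. The starting figure of 70 does not. The normal formula gives n = 2 × [(1.960 + 0.842)/0.30]² = 174.4 per arm, and the t-test gives 175.4, or 176.

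**2. What would give 70.** The variance factor needed is 70/174.4 = 0.401.
- Mean of 3 visits, factor (1 + 2ρ)/3: ρ ≈ 0.10.
- Mean of 4 visits, factor (1 + 3ρ)/4: ρ ≈ 0.20.
- Mean of 3 follow-ups with baseline as covariate, factor (1 + 2ρ)/3 − ρ²: ρ ≈ 0.54.
- One visit with baseline as covariate, factor 1 − ρ²: ρ ≈ 0.77.
- One visit as change from baseline, factor 2(1 − ρ): ρ ≈ 0.80.

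The first three are time-averaged effects. A single visit gets there only with a high baseline correlation.

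**3. Power for d = 0.30 with an effective 70 per arm.**

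| Comparison | ρ = 0.3 | ρ = 0.5 | ρ = 0.7 |
|---|---|---|---|
| One visit, unadjusted | 42% | 42% | 42% |
| One visit, baseline covariate | 46% | 53% | 69% |
| One visit, change score | 32% | 42% | 62% |
| Time-by-treatment, 3 df, constant effect | 31% | 42% | 65% |

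The interaction row has baseline in the model as a fourth time point. Its noncentrality is (70/2) × 0.30² × 3/[4(1 − ρ)], which is 3.4, 4.7 and 7.9.

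Seventy is the number left after 12-month attrition. At 4 months with nobody lost (94 EUC and 138/1.48 = 93 effective bCBT), unadjusted power is about 53%.

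**4. Detectable differences at one visit.** With 70 per arm, the t-test detects 0.477 SD at 80% power. The last column multiplies by √(1 − 0.5²) = 0.866.

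| Outcome (SD) | Stated | 0.30 × SD | One visit, unadjusted | Baseline covariate, ρ = 0.5 |
|---|---|---|---|---|
| PHQ-9 (6.1) | 1.83 | 1.83 | 2.9 | 2.5 |
| BDI (12) | 3.6 | 3.6 | 5.7 | 5.0 |
| MCS (11.5) | 3.45 | 3.45 | 5.5 | 4.75 |
| MCS (14.7) | – | 4.41 | 7.0 | 6.1 |
| PCS (11) | 3.3 | 3.3 | 5.2 | 4.5 |
| PCS (12) | – | 3.6 | 5.7 | 5.0 |

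For both MCS and PCS, the stated figure uses only the smaller cited SD.

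**5. Power for 5 points on the SF-12 at one visit, unadjusted.** MCS: 72% (SD 11.5) and 52% (SD 14.7). PCS: 76% (SD 11) and 69% (SD 12).

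**The case against.** The plan says that the number was adjusted for repeated measures and cites a source, so 70 is not shown to be a miscalculation. Several conventional settings give it. That stands: the fault is a missing input and a mismatch with the stated comparisons.

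A reader might infer that every stated detectable difference is too small. The documents do not support that. For the baseline-adjusted average of the three follow-ups, the requirement peaks at 174.4 × 4/9 = 77.5, or 78 per arm (at ρ = 1/3). Power with 70 therefore stays at about 75% or more whatever the correlation, and at the smaller SDs the stated differences are met or nearly met. The unadjusted average is more fragile: it needs 94, 117 and 140 per arm at ρ = 0.3, 0.5 and 0.7.

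A reader might also infer that a repeated-measures saving exists only for an average over visits. That is wrong too, since a baseline measure also helps a single visit, by the factor 1 − ρ². The quality-of-life shortfall is correspondingly smaller if baseline is used. At ρ = 0.5 only MCS with SD 14.7 stays clearly above 5 points.

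Nor is the depression conclusion in danger at the plan's own benchmark. Unadjusted single-visit power for 5 PHQ-9 points is above 99%. The statement about a 50% BDI reduction is also safe: read as 10 points between arms from a mean of 20, with SD 12, its power is above 99%.

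**Conclusion.** The concern holds in a limited form. Seventy per arm cannot be reproduced without a correlation that the plan does not give, and at plausible correlations it fits a time-averaged effect. It does not support 80% power at 0.30 SD for the comparisons that Aim 2 names, unless the correlation with baseline is about 0.77 (covariate) or 0.80 (change score) or higher. Below that, power at a visit is 42% unadjusted and 46–69% with a baseline covariate over the assumed range 0.3–0.7. The interaction has 31–65% over the same range if the effect is constant.

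The stated differences hold, or nearly hold, only for a time-averaged and preferably baseline-adjusted contrast. Without adjustment, the single-visit values are about 1.6 times as large at the same SD (0.477/0.30). The claim of more than 80% power for a 5-point quality-of-life difference is not supported at a single unadjusted visit.

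The unadjusted single-visit figures use only numbers in section 5.6. All others rest on assumed correlations and compound symmetry. Nothing here shows that 232 is the wrong sample size for every contrast.

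**What to change.** Keep the sample at 232 and rewrite the power paragraphs of section 5.6:
- Name the contrast to which 0.30 and 80% refer, for example the baseline-adjusted average over 4, 8 and 12 months. Give the number of measures, the assumed within-patient correlation and any baseline adjustment, and make the Aim 2 model match.
- Recompute the power for that contrast, and report power for the visit-specific and interaction comparisons over a range of correlations.
- List single-visit detectable differences, using both cited SDs for MCS and PCS.
- Limit the quality-of-life power claim to the contrast and SD for which it holds.

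The cost is wording and a short recalculation, with no extra patients. The downside is that the stated figures become less favourable.

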The bCBT intervention will be delivered by VA CBOC clinicians at the Houston and Oklahoma City affiliated CBOCs. All mental health clinicians at the 16 CBOC sites will be approached for inclusion in the study. We anticipate that a minimum of 12 clinicians will be enrolled, with a realistic estimate to approach 15 or more enrolled clinicians before the end of the trial, given staff turnover and program expansion efforts. Clinicians will receive online bCBT training with an emphasis on care for Veterans in the CBOC setting. Clinicians will be invited to participate by referral from clinic directors and/or VISN 16 mental health leadership. The study team will follow-up with the clinician and his/her supervisor to verify that study participation is appropriate. CBOC clinicians will receive advocacy (when needed) from the study staff and VISN leadership (see Appendix 2, letters of support) to resolve barriers to participation. Clinicians will not be restricted based on discipline or prior CBT experiences, but will be expected to have an interest in obtaining training and willingness to use bCBT in their practice. As seen in our ongoing trial, we anticipate that nurses, social workers, psychologists, counselors, and physician assistants will participate. The study team will try to work with clinicians to receive workload credit, but will not guarantee.

All enrolled clinicians will receive a series of training and facilitation tools to assist their use of bCBT in their VA care settings. The proposed implementation strategy (training and facilitation tools) will be based on our prior work as outlined by Mignogna, et al. 2014.²² The proposed implementation strategy will initially include a series of techniques but will be modified with input from CBOC stakeholders during the development and refinement process. The initial strategy will include the following facets:

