5.2 Recruitment Methods

Clinician Participants

Clinicians will be VA employees working as mental health clinicians at CBOC facilities. All VA mental health clinicians at the 16 CBOC sites will be approached for inclusion in the study. No contract CBOCs or contract mental health providers will be approached. We anticipate that a minimum of 12 clinicians will be enrolled, with a realistic estimate, given staff turnover and program expansion efforts, to approach 15 or more enrolled clinicians before the end of the trial. Clinicians will be invited to participate by referral from clinic directors and/or VISN 16 mental health leadership (see Appendix 4, Clinician Recruitment Letter). The study team will follow-up with the clinician and his/her supervisor to verify that study participation is appropriate. Study staff will follow up with the clinician via email to confirm interest. If there is no response to the email a follow up phone call will be placed. CBOC clinicians will receive advocacy (when needed) from the study staff and VISN leadership (see letters of support) to resolve barriers to participation. Clinicians will not be restricted based on discipline or prior CBT experiences but will be expected to have an interest in obtaining training and willingness to use bCBT in their practice.

[figure not shown]
Veteran Participants

Based upon sample-size calculations (including attrition over time), the total sample to be randomized is 232. Participants are not randomized until after conformation of depression after the baseline. Because final determination of study inclusion cannot be determined until the baseline appointment, we anticipate needing to provide consent to approximately 300 Veterans total. Approaching Veterans who are not necessarily treatment seeking is a critical component of the project and allows for increased reach to Veterans who might otherwise go unrecognized by the healthcare system. The recruitment procedures comprise four stages designed to maximize reach while minimizing participant burden and confusion about study procedures.

Local Advisory Council Participants

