Minimization of Attrition: Improved engagement and retention of participants may be challenging for Veterans cared for in CBOC settings but our experiences using telephone-based recruitment procedures in prior trials have been highly successful. A 25% attrition rate was used for study-power calculations, which is slightly above our current trial's attrition rate of 22%. Dropouts will include any participants who indicate a desire to withdraw from the study following random assignment. Reasons for study discontinuation will be recorded for subsequent analyses; and overall attrition rates will be examined as a primary study aim. The current proposal employs a flexible intervention approach, using individual sessions and telephone encounters to decrease attrition and improve participant engagement and adherence to treatment. We will also minimize attrition by reducing our "research presence" by using telephone assessments and limited research contact following randomization, and modestly compensating participants for their time. Additionally, Veterans that become difficult to contact via telephone will be mailed an unable to reach letter to encourage them to contact the study (see Appendix 10). The letter will explain the team's efforts in trying to contact them and ask the Veteran to follow up with study staff to schedule an appointment.

Note: bCBT patients who drop out of treatment will be allowed to continue with research follow-up assessments.

Analyses:

Aim 1 analyses will use data from the mixed-method formative evaluation described above.

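### The clustering factor of 1.48 uses 5.8 patients per therapist and is not recomputed for the enlarged bCBT arm, so the stated 80% power is about 4 points high at 12 therapists, about 1 point high at 15, and sound from about 18

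*Combined protocol and SAP*

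**What the plan says.** The sample size part of 5.6 starts from 70 patients per arm for 80% power at 0.30 SD (two-sided .05, adjusted for repeated measures). It multiplies the bCBT arm by [1 + (m - 1)c], with m the patients per therapist and c the intraclass correlation: "Based on the sample size of 70 bCBT patients, an average of 5.8 patients per therapist, and an assumed correlation" of .10, so that "our inflation factor is 1.48" and 70 becomes 104. EUC receives no clustering factor. Then "Both the bCBT and EUC groups are inflated to account for attrition rate at 12 months of 25" per cent, "resulting in 138 patients for bCBT and 94 for EUC".

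On that basis 5.6 claims: "We will have 80% power to detect a clinically important difference in means on the PHQ-9" as small as 1.83. It also prints detectable differences of 3.6 (BDI), 3.45 (SF-12 MCS) and 3.3 (SF-12 PCS).

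The therapist number appears elsewhere. Section 5.1 says: "We anticipate that a minimum of 12 clinicians will be enrolled, with a realistic estimate to approach 15 or more enrolled clinicians", and 5.2 repeats the minimum of 12, "with a realistic estimate, given staff turnover and program expansion efforts, to approach 15 or more enrolled clinicians before the end of the trial". Section 5.3 counts 24 mental health clinicians currently serving the 16 clinics.

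**The concern.** In this formula m is the cluster size in the sample that is analysed. If the number of therapists is fixed, enlarging the arm by 1.48 also enlarges every caseload, so the factor that justified the enlargement is no longer large enough. The plan applies the factor once and stops. A caseload of 5.8 can hold for both 70 and 104 patients only if the therapist number grows with the arm, and 5.6 says nothing about that.

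At stake is the accuracy of the power statement. The 80% and the four detectable differences are printed without a therapist number, although they depend on it and clinician enrolment was uncertain. A reader judging the trial's sensitivity, especially after a null result, would want to see that dependence.

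**Working it through.** **Reproducing the plan.** 1 + (5.8 - 1) x 0.10 = 1.48. 70 x 1.48 = 103.6, printed as 104. 103.6/0.75 = 138.1 and 70/0.75 = 93.3, giving 138 and 94, total 232. The chain reproduces.

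**Where 5.8 comes from.** 5.6 does not give the divisor. 70/12 = 5.83 fits the sentence, which names the 70 patients, and the minimum of 12 clinicians. But 104/18 = 5.78 and 138/24 = 5.75 also round to 5.8. The check below does not depend on which was used.

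**Therapists needed for m = 5.8.** Evaluable bCBT patients: 138 x 0.75 = 103.5. 103.5/5.8 = 17.8, so about 18, or 18/24 = 75% of the clinicians counted in 5.3.

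**Power by number of therapists k.** Inputs from 5.6: c = .10, attrition 25%, evaluable 103.5 (bCBT) and 94 x 0.75 = 70.5 (EUC). Equal caseloads and a normal approximation are assumed. The base of 70 per arm = 80% at 0.30 SD is taken as given.

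- m = 103.5/k; factor = 1 + (m - 1) x 0.10; effective bCBT n = 103.5/factor
- R = sqrt[(1/effective n + 1/70.5) / (2/70)], the standard error relative to the plan's 70 v 70
- Detectable difference at 80% power = 0.30 x R
- Power at 0.30 SD = Φ(2.802/R - 1.960), where 2.802 = 1.960 + 0.842

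Example, k = 12: m = 8.625; factor 1.763; effective n = 58.7; R = sqrt[(0.01704 + 0.01418)/0.02857] = 1.045; detectable 0.314 SD; power Φ(0.72) = 76.4%.

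| k | m | Factor | Effective n | Power | Detectable (SD) | PHQ-9 (SD 6.1) |
|---|---|---|---|---|---|---|
| 12 | 8.6 | 1.76 | 58.7 | 76% | 0.314 | 1.91 |
| 15 | 6.9 | 1.59 | 65.1 | 79% | 0.305 | 1.86 |
| 18 | 5.75 | 1.48 | 70.2 | 80% | 0.299 | 1.83 |
| 24 | 4.3 | 1.33 | 77.7 | 82% | – | – |

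Power crosses 80% at 17.6 therapists.

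**Lower attrition.** Section 5.6 notes: "A 25% attrition rate was used for study-power calculations, which is slightly above our current trial's attrition rate of 22" per cent. At 22% (107.64 v 73.32 evaluable), power is 78%, 80% and 81% at 12, 15 and 18 therapists, and the break-even is 15.2.

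**Patients who never start bCBT.** Section 5.3 plans interviews with patients who completed no sessions, but no rate is given. Such patients are not clustered by therapist. With non-starter share p, the factor is 1 + (m(1 - p) - 1) x 0.10 x (1 - p). Holding 0.30 SD fixed, an assumed p = 10% gives 78%, 80% and 82%. The shortfall disappears at p of about 8% with 15 therapists and about 19% with 12.

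**SF-12 differences.** 5.6 cites SDs of 14.7 and 11.5 for MCS and of 11 and 12 for PCS. The printed values use the smaller: 0.30 x 11.5 = 3.45 and 0.30 x 11 = 3.3. The larger give 0.30 x 14.7 = 4.41 and 0.30 x 12 = 3.6. These two figures are therefore incomplete at any therapist number.

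**The case against.** The strongest reply is that the plan allows for 18. Its realistic figure is open-ended (15 or more), it cites turnover and program expansion, and all mental health clinicians at the 16 clinics are to be approached, from a pool of 24. That stands. A reader might infer that the printed 80% fails at every therapist number the plan contemplates; the documents do not support this. Nor do they establish that 5.8 is 70/12, since two other divisions fit.

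Second, the effect is small where the plan expects to be. At 15 therapists it is about 1 point of power, or 0.03 PHQ-9 points, and either 22% attrition or a modest share of non-starters removes it. This also stands; the 4-point figure belongs to the stated minimum of 12 with every patient starting treatment.

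Third, the base of 70 per arm cannot be verified. Without the repeated-measures adjustment about 175 per arm would be needed, and 5.6 gives no correlation. With three equally correlated follow-ups (an assumption), 70 per arm gives 80% at a correlation of .10, 74% at .20, 68% at .30 and 58% at .50. That uncertainty is larger than the correction here and limits it to whole points. It does not make 1.48 the right factor for 104 patients: the comparison is made on the plan's own base.

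Fourth, the mixed model in 5.6 lists no therapist term, so these figures, like the plan's, describe a clustering-adjusted comparison of means. That is true, and it is a separate matter.

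Finally, the document is dated January 2018 and first enrolment was anticipated in March 2015, so a table over hypothetical therapist numbers may come late. If the number is already known, the correction is simpler, not unnecessary.

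**Conclusion.** The point holds as a correction to the stated justification. The 1.48 is tied in the text to the arm before inflation and is not updated. On the plan's own ICC and attrition, power for 0.30 SD is about 76% at the stated minimum of 12 therapists, about 79% at 15, and 80% or more from about 18. The shortfall is therefore about 4 points, about 1 point, and none. This rests on 70 per arm giving 80%, equal caseloads, c = .10, and every bCBT patient being treated by a therapist. Unequal caseloads would lower power further; lower attrition or non-starters would raise it.

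A reader might conclude that the trial is underpowered and the target must rise. The documents do not support that. The size of the loss depends on a therapist number that 5.6 does not fix, and the loss is small at the realistic figure. The detectable PHQ-9 difference stays at or below about 1.9 points, against the 5 points the plan calls clinically relevant. Even with the larger MCS SD at 12 therapists it is 0.314 x 14.7 = 4.6, still under the plan's 5-point threshold for quality of life.

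**What to change.** In 5.6, compute m from the evaluable bCBT arm (138 x 0.75 = 103.5) and a stated number of therapists, and replace the single 1.48 / 80% statement, for example with:

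> With 103.5 evaluable bCBT patients, the average caseload is 8.6, 6.9 or 5.8 for 12, 15 or 18 therapists. At c = .10 the clustering factor is 1.76, 1.59 or 1.48, and power for 0.30 SD is about 76%, 79% or 80%.

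Restate the detectable differences beside it, showing both SDs cited for each SF-12 score:

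| Therapists | PHQ-9 | BDI (SD 12) | MCS (SD 11.5 / 14.7) | PCS (SD 11 / 12) |
|---|---|---|---|---|
| 12 | 1.9 | 3.8 | 3.6 / 4.6 | 3.4 / 3.8 |
| 15 | 1.9 | 3.7 | 3.5 / 4.5 | 3.4 / 3.7 |
| 18 | 1.8 | 3.6 | 3.4 / 4.4 | 3.3 / 3.6 |

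If the number of treating clinicians is already known, add that case. Optional: rows for other ICC values (power 81 / 83 / 83% at an assumed .05 and 72 / 75 / 77% at an assumed .15, for 12 / 15 / 18 therapists) and the share of bCBT patients assumed to start treatment.

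The cost is one sentence and a small table, with a slightly less favourable power statement below 18 therapists. The target of 232, the 138:94 allocation, recruitment and design do not change.
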